10.2.1.1 Study visit: Month 6 (Day 169 \pm 3 days)

After all Month 6 assessments pertaining to the main study have been made and the subject has been confirmed to be eligible to proceed in the extension study (see section 9.2), the subject will be requested to sign the extension-specific ICF that she was given at the Month 5 visit.

Note: inclusion in the extension study will not be postponed if the results of any Month 6 assessment are not available on the day of Month 6 visit. Subjects will be required to stop the treatment if the results obtained after enrollment meet the discontinuation criteria defined in Section 10.7.2.1.

After signature of the extension-specific ICF, the subject will be dispensed new treatment kits. The subject will take her daily dose of study medication at the study site from these newly dispensed kits. The exact time of dosing (hour/minute) will be recorded in eCRF.

In addition, the subject will:

- receive contraception counselling and will be given double barrier contraception (condoms with spermicide), if requested, to be used until 3 months after treatment end. If the subject is at risk for

acquiring HIV, she must be reminded to use double non-hormonal barrier contraception without spermicides (eg: condoms and diaphragms).

- be provided/prescribed a limited quantity (as per Investigator's judgement) of standard doses of permitted analgesics as rescue medication for EAP for the duration of the study.
- receive calcium 500 to 1000 mg and vitamin D 400 IU supplementation

Upon completion of the visit, the subject will be provided with emergency contact phone numbers and will be scheduled for her next visits.

10.2.1.2 Study visits: Month 7 (Day 197 -3/+2 days) and Month 8 (Day 225 ± 3 days)

The following tests and evaluations will be performed :

- eDiary completion compliance check
- ePRO and ClinRO completion, ideally before any other procedures or assessments:
 - at Month 7 visit: EHP-30, EQ-5D-5L, PROMIS, mPGIS, PGIC, HRUQ, HRPQ with mPGIS and PGIC completed last
 - at Month 8 visit: mPGIS, PGIC, HRUQ and HRPQ with mPGIS and PGIC completed last.
- Concomitant treatments recording
- AE recording
- Completion of the paper C-SSRS questionnaire (version for "already enrolled subjects" (see Appendix S) for patients responding to the C-SSRS for the first time during the study, or version "since last study visit" (see Appendix T) for patients for whom the C-SSRS was completed at the previous study visit)

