- ECG: subjects who have a QTcF > 500 ms at the Month 6 assessment or increase > 60 ms from the highest value prior to the first dose in the main study

2. **Per Protocol Extension Analysis Set (PP EAS)**: All subjects from Treatment Extension Analysis Set, excluding those identified as having major protocol deviations that could potentially affect the efficacy assessments up to Month 12. Subjects will be analyzed according to randomized treatment.

3. **Follow-up Extension Analysis Set (FU EAS)**: All subjects from the main study who entered the extension study and received at least one dose of study drug with the exception of subjects whose Month 6 assessment subsequently met any of the discontinuation criteria, and who entered the Post-Treatment Follow-Up Period. Subjects will be analyzed according to randomized treatment.

4. **Extension Safety Analysis Set (ESAF)**: All subjects randomized into the extension study who received at least one dose of study drug irrespective of the treatment received. Subjects will be analyzed according to treatment received.

5. **Follow Up Safety Analysis Set (FU SAF)**: All subjects randomized into the extension study who received at least one dose of study drug irrespective of the treatment received, and who entered the Post-Treatment Follow-Up Period. Subjects will be analyzed according to treatment received.

6. **Extension Pharmacokinetic (PK) Set**: all subjects who were randomized and received active study medication in the main study, had no major protocol deviations impacting PK throughout the main study or extension and with available PK data. Subjects will be analyzed according to treatment received.

7. **Extension Pharmacodynamic (PD) Set**: all subjects who were randomized and received active study medication in the main study, had no major protocol deviations impacting PD throughout the main study or extension and with available PD data. Subjects will be analyzed according to treatment received.

In general, analyses of efficacy will be conducted using the TEAS, PP EAS (when specified) and FU EAS sets, analyses of safety will be conducted using the ESAF and FU SAF, and analyses of PK and PD will be conducted using the PK and PD Sets accordingly.

The actual treatment will be derived as follows, based on daily e-diary IMP intake data:

Treatment kits will be dispensed to the subjects as follows:

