5.5. Visit Windows

For all analyses except for the DXA assessments and the diary questionnaires, the visits as collected in the eCRF will be used.

The rules for visit day calculations are listed in Table 1 below.

E-diary questionnaires:

For diary questionnaires (EHP-30, EQ-5D-5L, HRPQ, HRUQ, PGIC, PPGIC, PGIS, PROMIS, SSIQ) except for the PSIQ, the e-diary dates of assessment of each visit will be checked versus the dates of same visit in eCRF to handle for e-diary visit errors. Only assessments within the window of the date of eCRF+/-14 days will be used in analyses. In case of multiple assessments falling within the same window of an eCRF date, the non-empty record with completion date closest to the eCRF date will be used.

Due to the war situation in Ukraine, some subjects from Ukraine sites may have completed visits and e-diary questionnaires but not collected the data in the eCRF. For all ediary questionnaires data of subjects from Ukraine sites with a later questionnaire date of 24FEB2022, the e-diary dates will be compared to theoretical visits dates instead of eCRF visits dates if eCRF dates are missing.

For data from discontinued visits, the discontinuation visit date should be compared to theoretical visit dates. Only assessments within the window of theoretical date +/-14 days will be used for analyses, if it is planned to have a such assessment at this visit and no other assessment is in the window. If a subject discontinued in the extension treatment period, date will be compared to the theoretical visit dates in the extension treatment period as described in Table 1. If a subject discontinued in the extension follow-up period, date will be compared to the theoretical number of the theoretical visit dates in the extension follow-up period, date will be compared to the theoretical number of the theoretical visit dates in the extension follow-up period, date will be compared to the theoretical number of the theoretical visit dates in the extension follow-up period, date will be compared to the theoretical visit dates in the extension follow-up period, date will be compared to the theoretical visit dates in the extension follow-up period, date will be compared to the theoretical visit dates in the extension follow-up period, date will be compared to the theoretical visit dates in extension follow-up period from Table 2.

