Note that assessments from discontinued visits in **Example** eDiary device are entered under Month 12 (Month 6 Extension FU in follow-up). They will be recoded as discontinued visits before applying the windowing rules.

Pharmacokinetics data

Visit windows rules for PK data will be the following:

- PK assessments will be included in analysis if:
 - Assessment is Pre-dose (or PK time = dose time), or IMP intake is not done on the day of PK sampling (i.e. considered as pre-dose), and,
 - PK assessment date is within +/-10 days of the theoretical visit and up to 2 days after last IMP intake for Month 12 visit.

If the PK sampling time is missing, or the IMP intake on the same day is done and the IMP intake time is missing then assessments will not be included.

IMP intake status (done/not done) and IMP intake time from the Pharmacokinetics eCRF page will be used.

PK samples analysed after the period of long term stability will be excluded.

DXA data

Visit windows rules for DXA assessments will be the following:

- The DXA assessment at Month 9 will be derived as the first non-missing DXA assessment with acceptable quality (accepted="Yes") and dated between Month 9 theoretical date (=Day 253) -28 days and Month 9 theoretical date + 28 days.
- The DXA assessment at Month 12 will be derived as the first non-missing DXA assessment with acceptable quality (accepted="Yes") and dated between Month 12 theoretical date (=Day 337 in the main study) -28 days and Month 12 theoretical date + 28 days.
- The DXA assessment at Month 6 Extension Follow-Up will be derived in the same way as the DXA assessment at Month 12. Theoretical date of Month 6 Extension Follow-up is 168 days after Month 12 theoretical date or after treatment discontinuation.

Other safety data:

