6.2. General Statistical Methods

6.2.1. **General Methods**

All output will be incorporated into Microsoft Excel or Word files, sorted and labeled according to the International Conference on Harmonisation (ICH) recommendations, and formatted to the appropriate page size(s).

Tabulations will be produced for appropriate demographic, baseline, efficacy, pharmacokinetic and safety parameters.

The analyses will be performed on 4 treatment groups (taking into account the treatment taken in the main study):

- linzagolix 75 mg / linzagolix 75 mg
- linzagolix 200 mg with ABT / linzagolix 200 mg with ABT
- Placebo / linzagolix 75 mg (subject receiving placebo in main study and treated with linzagolix 75 mg in extension study)
- Placebo / linzagolix 200 mg with ABT (subject receiving placebo in main study and treated with linzagolix 200 mg with ABT in extension study)

For continuous data and for ordered categorical data, if appropriate, the number of non-missing observations, mean, standard deviation, median, first and third quartiles, minimum and maximum will be calculated, including for change from baseline when applicable.

The baseline mean will be calculated for all subjects based on the Extension Safety Analysis Set

For efficacy endpoints and BMD, a baseline mean will also be calculated for each visit using the baseline data for the subset of subjects who attended that visit, such that the same subjects contribute to the mean for the visit and the mean for the corresponding baseline values. Summary

CRS-BS-TP-000005 V 2.0

statistics will be based primarily on non-missing values. For ordered categorical data and nominal data, absolute counts and relative frequencies (in %) will be calculated.

Raw and derived data will be listed.

6.2.2. **Definition of Baseline**

The baseline will be described in two ways:

- Main Baseline (named Baseline), defined in the Statistical Analysis Plan of the main study and calculated according to first dose of IMP taken during the main Study.
- Second Baseline (named Baseline 2), defined as the last assessment before the first active dose of IMP during the extension study. For efficacy endpoints based on daily diary data, the Baseline 2 will be based on the last 28 days prior to and including last treatment administration in main study.

The baseline 2 will be calculated only for the subjects who are in the placebo arm (actual arm) in the main study.

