6.6. Safety Evaluations

Summaries will be performed using the Extension Safety Analysis Set and the Follow-up Extension Safety Analysis Set.

Data from the main study (i.e. before Month 6), the extension study and the Month 6 Extension follow-up will be summarized and listed as relevant

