6.6.2. Bone Mineral Density (BMD) by DXA

BMD of femoral neck, total hip and lumbar spine will be assessed by DXA at Baseline, Month 9 (if required) Month 12 and Month 6 of the extension follow-up (if required). Unacceptable DXA assessments (accepted="No") will not be summarized (hip, spine and femur considered separately).

In case of repeated values due to BMD loss ≥5%, the initial scan will be used in summaries. Initial and repeated scan values will be reported in the listings.

Calibrated values will be used if available, otherwise initial values will be considered.

BMD, expressed as both absolute values and Z-scores will be summarized at each visit in terms of actual values, changes from baseline, changes from baseline 2 (only for the subjects who are

in the placebo arm in the main study) for each anatomic location. For absolute values only, percent change from baseline, percent changes from baseline 2 (only for the subjects who are in the placebo arm in the main study) and 95% confidence interval for the mean percent change from baseline and for the mean percent change from baseline 2 within each group will be produced at each time point.

The definition of both baselines are described in section 6.2.2.

Percent change from baseline and percent change from baseline 2 to Month 9, Month 12 and Month 6 extension follow-up will be described and will also be summarized in categories of percentage with the following classes:

- No change or increase,
- Decrease $\leq 3\%$,
- Decrease > 3% and $\leq 5\%$,
- Decrease > 5% and \leq 7%,
- Decrease > 7% and \leq 8%,
- Decrease > 8%.

All data except unacceptable DXA measurements (accepted="No") will be listed.

Due to the war situation in Ukraine, data from subjects in Ukraine sites may be incomplete, missing or uncleaned. A sensitivity analysis of the BMD will be performed, excluding data collected after 24FEB2022 for subjects from Ukraine sites. An additional listing including subjects from Ukraine only will be provided.

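### Month 12 DXA is placed by date and scan quality only, so a very early stopper's scan about 24 weeks off drug also enters the Month 12 BMD rows, while withdrawal scans on Days 282–308 enter none

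*SAP*

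**What the plan says.** SAP 5.5 treats DXA as an exception to visit labels: "For all analyses except for the DXA assessments and the diary questionnaires, the visits as collected in the eCRF will be used". For Month 12, "The DXA assessment at Month 12 will be derived as the first non-missing DXA assessment with acceptable quality" and a date within 28 days either side of Day 337. Month 9 follows the same pattern around Day 253. Month 6 extension follow-up (ExFU) is derived like Month 12, and "Theoretical date of Month 6 Extension Follow-up is 168 days after Month 12 theoretical date or after treatment discontinuation". The DXA rules contain no limit on time since last dose and do not confine a scan to one visit. The PK rule just above them does: it limits Month 12 samples to 2 days after the last intake.

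On tables and populations, SAP 6.6.2 states "Percent change from baseline and percent change from baseline 2 to Month 9, Month 12 and Month 6 extension follow-up will be described", together with loss categories. SAP 6.6 adds: "Summaries will be performed using the Extension Safety Analysis Set and the Follow-up Extension Safety Analysis Set". The Extension Safety Analysis Set in SAP 4.1 is "All subjects randomized into the extension study who received at least one dose of study drug irrespective of the treatment received". Baseline 2, for women who had placebo in the main study, is "defined as the last assessment before the first active dose of IMP during the extension study".

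On conduct:
- Protocol 10.7.2 requires the Month 12 procedures at withdrawal from treatment, but waives the DXA before the Month 9 visit. It waives the exit DXA for women who leave follow-up before Month 3 ExFU.
- Protocol 10.2.2.3 sets the final follow-up visit of an early stopper at 168 ± 7 days after last intake, with the DXA within 10 days of that visit.
- Protocol 10.4.6 describes the Month 12 DXA as the end-of-treatment scan.
- Protocol 10.2.1.1 lets women enter before all Month 6 results are in: "Subjects will be required to stop the treatment if the results obtained after enrollment meet the discontinuation criteria".

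**The concern.** BMD change is the first listed safety endpoint, and a reader will take its Month 12 row as bone status at the end of treatment. Under the date rule, that row can also hold scans taken about 24 weeks after the last dose. In a placebo-switch group, such a Month 12 change from Baseline 2 would follow only a few weeks of active drug. The same scan is also counted, correctly, as Month 6 ExFU.

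The design makes such women foreseeable. Some must stop soon after entry because a late Month 6 result meets a discontinuation criterion, and SAP 4.1 lists BMD loss above 8% among those criteria. They leave the efficacy set but stay in the safety set that the BMD tables use.

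At the other end, a woman who withdraws between the two windows has a required scan close to her last dose, and no summary row takes it.

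**Working it through.** Let T be the study day of the last extension dose. Inputs are from SAP 5.5 (windows and Tables 1–2), Protocol 10.2 (visit days), 10.2.2.3 (follow-up tolerances) and 10.7.2 (withdrawal DXA).

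**1. Reproduce the plan's days.** Month X = 1 + 28X gives Day 169 (Month 6), 253 (Month 9) and 337 (Month 12). Also 337 + 168 = 505. All agree with SAP Table 1 and Protocol 10.2.

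**2. DXA windows.** Month 9: 253 ± 28 = Days 225–281. Month 12: 337 ± 28 = Days 309–365. Between them lie Days 282–308, which is 27 days.

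**3. When the end-of-follow-up scan falls in the Month 12 window.** The scan is due at T + 168. The tolerances add up to 7 + 10 = 17 days either way, so it falls between T + 151 and T + 185 (21.6 to 26.4 weeks off drug).

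| Case | Condition | Last dose T | Extension doses (T − 169 + 1) |
|---|---|---|---|
| Nominal timing | T + 168 ≤ 365 | 169–197 | 1–29 |
| Possible with tolerances | T + 151 ≤ 365 | up to 214 | up to 46 |
| Certain if the scan is on schedule | T + 185 ≤ 365 | 169–180 | 1–12 |

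At nominal timing the scan falls on Days 337–365. The 46 doses become 43–49 once the ± 3 days on the Month 6 visit are allowed for. From T = 215 onward, a scheduled end-of-follow-up scan cannot reach the window.

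**4. Double use.** The Month 6 ExFU window for the same woman is T + 140 to T + 196. It contains the whole range T + 151 to T + 185, so every scan caught in step 3 fills both rows.

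**5. Exit scans from follow-up.** A woman who leaves after Month 3 ExFU has her exit DXA at T + 84 or later (nominal). It can fall in the Month 9 window if T + 84 ≤ 281, so T ≤ 197. It can fall in the Month 12 window if T + 84 ≤ 365, so T ≤ 281. If taken before T + 140 it is too early for Month 6 ExFU, and the on-treatment row is the only one it enters.

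**6. The gap.** A withdrawal scan on Days 282–308 also misses the woman's own Month 6 ExFU window, which opens on Day 422 for T = 282 and Day 448 for T = 308. The ± 14-day rules later in SAP 5.5 do not help. They cover other safety data, unscheduled assessments, and DXA labelled to a main-study follow-up visit. Even if applied, they would give Days 239–267 and 323–351.

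**7. Size.** The documents give no count of affected women, so the figures below rest on assumptions.
- *Arm mean:* shift = fraction affected × difference between those scans and the rest. For an assumed 1–5%, this is 0.01–0.05 points per 1-point difference. For scale only, the Phase 2b 75 mg fixed-dose arm at Week 52 (lumbar spine, Protocol 5.5.3) has a confidence-interval half-width of 2.21 − 1.139 = 1.071 points.
- *Loss categories:* if the planned 288 entrants split 96/96/48/48 and all were scanned, one scan is 1/96 = 1.04 percentage points in a continuing group and 1/48 = 2.08 in a placebo-switch group.

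**The case against.** The strongest defence is that summarising BMD by calendar time in everyone dosed is a legitimate safety display, and that the rows are named by month rather than as end of treatment. On that view, leaving a scan on Days 282–308 to the listings is ordinary windowing.

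The numbers may also be tiny, or zero. A woman must stop within the first weeks, remain about 24 weeks in follow-up, and have an accepted scan. The nearest figure in the documents is 12 of 176 (6.8%) stopping for adverse events over the 28-week Phase 2b extension (Protocol 5.5.3). Spread evenly, which is an assumption, that is 6.8% × 4/28 ≈ 1% in the first four weeks, before requiring completed follow-up. It does not count stops for late Month 6 results. BMD is descriptive here, no hypothesis is tested, and accepted scans and exposure are listed.

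The points on size stand. The calendar-time argument stands only in part: it does not explain why one scan should fill two visit rows when the SAP itself defines 168 days after discontinuation as Month 6 ExFU. It also sits badly with Protocol 10.4.6, which ties the Month 12 scan to the end of treatment.

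A reader might go further and infer that the Month 12 BMD results are materially biased, or that every early withdrawal contaminates them. The documents support neither. There is no count, and the direction is unknown: time off drug and selection of women with large losses could pull in different ways. Step 3 confines the end-of-follow-up problem to last doses up to Day 214.

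**Conclusion.** The defect is real and narrow. Applied as written, the SAP places a scan taken about 168 days off drug (151–185 with tolerances) in the Month 12 row as well as the Month 6 ExFU row. This needs a last dose on Days 169–197, or up to Day 214 at the limit of tolerances, and a woman who stays in follow-up. Exit scans after Month 3 ExFU can enter the Month 9 or Month 12 row in the same way. Required withdrawal scans dated Days 282–308 are not summarised at all.

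The arithmetic rests only on stated days and tolerances, taking discontinuation as the day of last dose and Day 169 as the nominal extension start. Any statement of effect rests on the assumed 1–5% share and the assumed 96/96/48/48 split. On those assumptions arm means hardly move, and the loss categories in the two placebo-switch groups are the most sensitive. The SAP should be corrected, but nothing here suggests that the overall BMD conclusions would change.

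**What to change.** Amend the DXA derivation in SAP 5.5 and the tables in SAP 6.6.2:

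1. A scan assigned to Month 6 ExFU may not also fill Month 9 or Month 12.
2. A Month 9 or Month 12 scan must be dated no later than 28 days after the last extension dose. Flag excluded scans in the listing. The 28 days is a convention borrowed from the SAP's window half-width and has no bone-specific basis. This condition is needed as well as the first because an exit scan can precede the Month 6 ExFU window.
3. Add an end-of-treatment DXA row: the last accepted assessment dated on or after Day 225 and within 28 days of the last extension dose. Never use a Month 6 scan or its repeat. Where a scan was repeated for BMD loss of 5% or more, use the initial scan, as SAP 6.6.2 already states.

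**Cost.** Two conditions, one table row and a slightly smaller Month 12 n. On-schedule completers lose nothing. Their visits fall on Days 334–340 and scans may be up to 10 days earlier, so scans run over Days 324–340; last doses on Days 333–339 put the limit at Days 361–367. Off-schedule completers can lose late scans: Day 365 for a last dose on Day 336, Days 362–365 for Day 333, and Days 351–365 for Day 322 (322 + 28 = 350). Women who stop before Month 9 without a DXA have no value in the new row.

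**Direction to disclose.** If the early stoppers include women with large losses, removing their scans makes the Month 12 loss categories look more favourable. Report the number excluded by group. Note that their scans remain in the Month 6 ExFU row, except post-Month 3 exit scans dated before that window, which remain in the listings only.
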